	Day -28 to First Treatment	V1	V2	V3	V4	V5	V6	V7				
	W1	W3	W5	W7	W9	W11	W13	Until PD				
	D1	D15	D29	D43	D57	D71	D85					

Patient Reported Outcomes (PRO)

Assessments & Procedures	Screen-ing/ Base-line	Treatment Phase ( $\pm$ 3 days)							End-of-Treatment Visit	Safety Follow-up Visit		Long-term Follow-up	Notes				
	Day -28 to First Treatment	V1	V2	V3	V4	V5	V6	V7	Until PD	On the Day of or Within 7 Days of Decision to Discontinue	28 Days ( $\pm$ 5 Days) After Last Treatment	12 Weeks ( $\pm$ 2 Weeks) After Last Treatment	Every 12 Weeks ( $\pm$ 2 Weeks)				
		W1	W3	W5	W7	W9	W11	W13			D1	D15	D29	D43	D57	D71	D85
Patient interviews	X									X							Participants will be asked to participate in an interview performed by a third-party vendor. Participants will be selected from all sites in the USA, Germany, and Korea.
Tumor Assessments																	
Tumor evaluation /staging (CT scan/MRI/other established methods)	X					X			Q8W up to 12 months, then Q12W				X m	A brain CT/MRI scan should be done as clinically indicated at Screening. Confirmation of CR or PR should be performed preferably at the regularly scheduled assessment intervals, but no sooner than 4 weeks after the initial documentation. See Section 8.1.1. The IRC should confirm measurable disease before enrollment as well as verify unconfirmed PD by Investigator read.	m In case treatment is discontinued due to another reason than PD, tumor assessments should be continued according to original protocol schedule until confirmed PD.		
Subsequent anticancer therapy (any line)										X	X	X					
Survival follow-up n													X n	n Survival Follow-up will continue until each participant was followed up for at least 3 years after the End-of-Treatment.			

Assessments & Procedures	Screen -ing/ Base-line	Treatment Phase (± 3 days)							End-of-Treatment Visit	Safety Follow-up Visit		Long-term Follow-up	Notes			
	Day -28 to First Treatment	V1	V2	V3	V4	V5	V6	V7	Until PD	On the Day of or Within 7 Days of Decision to Discontinue	28 Days (± 5 Days) After Last Treatment	12 Weeks (± 2 Weeks) After Last Treatment	Every 12 Weeks (± 2 Weeks)			
		W1	W3	W5	W7	W9	W11	W13			D1	D15	D29	D43	D57	D71
PK, ADA and CCI																
PK and ADA sampling	See Table 2 for PK and ADA sampling times															

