### **7.1.2.3 Continuation of Study Intervention After Local Treatment of Disease Progression**

If disease progression is due to brain metastasis, participants may continue study interventions after local treatment of the brain lesions provided that the above criteria are met in addition to the following:

- PD is verified by the IRC.
- Brain metastases have been treated locally and are clinically stable for at least 2 weeks prior to reinitiation of study interventions.
- There are no ongoing neurological symptoms that are related to the brain localization of the disease (sequelae that are a consequence of the treatment of the brain metastases are acceptable).
- Participants must be either off steroids or on a stable or decreasing dose of  $\leq 10$  mg daily prednisone (or equivalent).
- Benefit-risk assessment to continue study intervention is favorable after consideration of any alternative treatment options as assessed by the Investigator.

In addition, if disease progression is mainly due to a metastatic lesion, which in the opinion of the Investigator may be treated with radiotherapy or surgically removed, participants may continue study interventions after the local treatment of such a lesion provided that:

- PD is verified by IRC.
- It has been at least 2 weeks and the participant has fully recovered from the surgery or radiotherapy.
- Benefit-risk assessment to continue study intervention is favorable after consideration of any alternative treatment options as assessed by the Investigator.

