### Best overall response (BOR)

Best overall response will be assessed based on the tumor response at different evaluation timepoints from the first study intervention until the first documented disease progression for RECIST criterion. Only tumor assessments performed before the start of any further anticancer treatment will be considered in the assessment of BOR. Clinical deterioration will not be considered as documented disease progression.

BOR can be defined as confirmed or unconfirmed, both definitions are provided below.

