### **Disease Control Rate (DCR)**

Disease Control Rate (DCR) is defined as the proportion of participants with BOR according to evaluation criteria of CR, PR, or SD out of the total number of participants.

Separate tables will be provided for confirmed and unconfirmed BOR. Each one will provide the number and percentage of participants with cBOR (respectively uBOR) of CR, PR, SD, Non-CR/Non-PD, PD, ND and NE as well as the ORR and the DCR. The ORR and DCR will be provided with a two-sided 95% CI using the Clopper-Pearson method (exact CI for a binomial

proportion as computed by default by the FREQ procedure using the EXACT option). Exact binomial test (1 sample) against the null hypothesis for the ORR will be calculated for confirmed BOR to determine whether the null hypothesis of an ORR  $\leq 10\%$  can be rejected.

The individual percentage of change in the sum of diameter since baseline will be displayed over time on a spider plot, together with the first occurrence of new lesion and the participant off treatment. The change in the sum of diameters between baseline and the best post-baseline assessment (i.e. minimum change since baseline) will be displayed on a waterfall graph. Note the sum of diameters includes all target lesions (longest diameter for non-nodal lesions and short axis for nodal target lesions)

The best percent change in sum of target lesion diameters will also be presented in a waterfall plot with confirmed BOR per IRC and investigator, PD-L1 in tumor cells and immune cells, **CCI**, **CCI** and **CCI** status.

For spider plots and waterfall plots, the percent change from baseline in the sum of diameters will be displayed for valid timepoint assessments, only. For the purpose of this analysis, a valid timepoint assessment is defined as a complete assessment of all target lesions reported at baseline. Further, split and coalesced lesions have to be taken into account appropriately to determine if a timepoint assessment is valid to derive the percent change from baseline in sum of diameters. All sum of diameters should be used, including the ones beyond first PD (for waterfall plot, the best post-baseline sum of diameters will be used even if occurring beyond PD). For waterfall plot, the percent change from baseline to 8-weeks assessment, as well as the percent change from baseline to the best post-baseline sum of diameters will be displayed for each participant.

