		
Censoring rules (details provided in body text):
 
 
- No event (PD or death)
 
- No baseline and/or post-baseline assessment
 
- Start of new anticancer treatment
 
- Event after two or more subsequent missing response assessments
 

Sensitivity Analysis 1: PFS counting all events (PD and death) regardless of the start of a new anticancer therapy and ignoring the number of missing evaluable tumor assessments before progression or death

Sensitivity Analysis 2: PFS as assessed by the Investigator

**Progression-Free Survival (PFS)** time is defined as the time from first administration of study treatment until the first documentation of progression of disease (PD) or death due to any cause, whichever occur first.

PFS = (date of PD or death or censoring – date of first administration of study treatment + 1)/30.4375 (months).

The following censoring rules will also be applied for the PFS computation:

- Participants with no event (PD or death) will be censored on the date of the last adequate tumor assessment
- Participants who do not have a baseline tumor assessment or who do not have any evaluable post-baseline tumor assessments will be censored at the date of first administration of study treatment unless death occurred on or before the time of the second planned tumor assessment (i.e. 16 weeks) in which case the death will be considered an event.
- Participants who start new anticancer treatment prior to an event will be censored on the date of the last evaluable tumor assessment before anticancer therapy is given.

Note: any systemic anticancer therapy, any anticancer surgery and any anticancer radiotherapy with exception of palliative bone radiotherapy will be considered as new/subsequent anticancer therapy and will lead to censoring.

- Participants with an event after two or more subsequent missing response assessments (i.e. no assessments in 112 days during the first 12 months of follow-up or 168 days after the first 12 months of follow-up) will be censored on the date of the last evaluable tumor assessment.

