## 14.7 Delayed Response

**Delayed response** will be defined as a documented objective response [CR or PR] that occurred after the initial progression of disease. For those participants, the duration of delayed response (DOdR) will be defined as:

DOdR = (date of end of objective response – date of objective response + 1)/30.4375 (months).

with end of response being the earliest date between PD occurring after response, death, start of new anticancer treatment or cut-off date.

Two listings for participants having a delayed response according to RECIST 1.1 as measured by IRC will be described will be provided:

- For tumor assessment including: participant identifier, age, sex, race, date of first and last study intervention, date(s) of imaging, sum of lesion diameters, percent change in target lesions from baseline, and overall response.

- For duration of response including: participant identifier, age, sex, race, date of first and last study intervention, date/study day of first PD, date/study day of first response (CR or PR), ongoing response at cutoff date (Y/N), date/study day of end of response (with reason for end of response being PD, death, new anticancer treatment), duration of delayed response.

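### The spider and waterfall plots have no stop at subsequent anticancer therapy, so shrinkage after later treatment could be shown as a participant's best change on study drug

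*SAP*

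**What the plan says.** SAP Section 14.1 specifies the plots in the text under Disease Control Rate. A sum is plotted only if its timepoint is valid, where "a valid timepoint assessment is defined as a complete assessment of all target lesions reported at baseline". Subject to that, "All sum of diameters should be used, including the ones beyond first PD", and "for waterfall plot, the best post-baseline sum of diameters will be used even if occurring beyond PD". The waterfall also shows each participant's change at the 8-week scan. One version sets the best change beside confirmed BOR (per IRC and per investigator) and PD-L1 status. Section 14.2 repeats the plots for investigator reads. The only date limit is the general data cut-off in Section 9.

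For the response endpoint in the same section, the rule is narrower: "Only tumor assessments performed before the start of any further anticancer treatment will be considered in the assessment of BOR". That sentence is worded for BOR and does not mention the plots.

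**The concern.** This is a single-arm trial, so a reader will take the waterfall as a picture of what the study drug did to each participant's tumors. The plan takes a minimum over all valid scans up to the cut-off and asks only whether the target lesions were measured. It does not ask what treatment the participant had received by then. A response to the next drug, or the removal or irradiation of a target lesion, could become the best change. The bar could then stand beside a confirmed BOR derived from a different and smaller set of scans, and it could also distort any apparent pattern by PD-L1.

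**Working it through.** **1. The plan's own design figure.** Protocol 9.2 gives N = 141, null ORR 10%, assumed ORR 18%, one-sided alpha 0.025, success at 22 responders and power 80%. Exact binomial check:

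- P(X ≥ 22 | 141, 0.10) = 0.0239. With 21 responders it is 0.0419, so 22 is the smallest passing count.
- P(X ≥ 22 | 141, 0.18) = 0.8007.
- The Clopper-Pearson interval for 22/141 is 10.0% to 22.7%.

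All agree with the protocol. None depends on the plot rule, because ORR is built from BOR.

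**2. Which scans count, side by side.**

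| Output (SAP section) | Scans after first PD | Stop at new anticancer therapy |
|---|---|---|
| BOR, ORR (14.1) | excluded | yes |
| PFS, primary rule (14.4); DOR by the same rules (14.5) | not applicable | yes; "any systemic anticancer therapy, any anticancer surgery and any anticancer radiotherapy with exception of palliative bone radiotherapy will be considered as new/subsequent anticancer therapy" |
| Delayed response (14.7) | included | yes; duration is measured "with end of response being the earliest date between PD occurring after response, death, start of new anticancer treatment or cut-off date" |
| Spider and waterfall (14.1) | included | none stated |

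Delayed response is the closest comparison. It also looks beyond progression, yet it ends at new therapy. The SAP therefore already separates post-progression data from post-therapy data, except in the plots.

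**3. Can such scans exist?**

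- After study drug stops: the Protocol 1.3 tumor-assessment note reads "In case treatment is discontinued due to another reason than PD, tumor assessments should be continued according to original protocol schedule until confirmed PD". It gives no stop at subsequent therapy. SAP Table 5 also has a row for events after new therapy has started, and Sensitivity Analysis 1 counts them.
- While study drug continues: under Protocol 7.1.2.3, if progression is mainly due to a metastatic lesion suited to surgery or radiotherapy, "participants may continue study interventions after the local treatment of such a lesion", subject to conditions. Protocol 7.1.2.2 keeps participants treated beyond progression on the scheduled tumor evaluations.

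**4. Direction.** Best change = 100 × (smallest post-baseline sum − baseline sum) / baseline sum. A minimum over a larger set of scans cannot be higher than over a subset. Adding post-therapy scans leaves a waterfall bar unchanged or makes it look better. The spider plot shows every point, so its later points may move either way.

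**5. Illustration (all values assumed).** Baseline sum 100 mm; 90 and 125 mm before new therapy; 80 and 60 mm after it.

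- SAP rule: 100 × (60 − 100)/100 = -40%.
- Stop at new therapy: 100 × (90 − 100)/100 = -10%.
- Range: if the lowest post-therapy sum were 90 mm or more, the bar would stay at -10%; at 80 mm it would be -20%; at 60 mm it is -40%.

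For a resected target lesion, suppose it held a share w of the baseline sum, is scored as 0 mm, and the other targets are unchanged. The bar is then -100w%: -20% for w = 0.2, -40% for w = 0.4. If the timepoint is instead ruled not valid, no point is plotted. The SAP does not say which applies.

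**The case against.** The case against is substantial.

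- The plots are descriptive. No test or decision rests on them, and the endpoints that matter have their own stop.
- Not every scan counts. The valid-timepoint filter may remove a scan on which a resected target lesion can no longer be measured.
- The routes are narrow. Continued imaging after stopping applies to stops for reasons other than PD. Protocol 7.1.2.3 first deals with brain metastases, and the other lesion it describes may be new or non-target and so outside the sum. Protocol 6.5.3 prohibits chemo- and radio-embolization during study treatment.
- Some disclosure is planned: the 8-week change, BOR beside the bars in one version, an off-treatment mark on the spider plot, and a tumor listing with the start of subsequent therapy.
- Using post-progression sums is a deliberate, prespecified choice.

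Most of this limits the size of the problem, and I accept it. It does not supply the missing stop. The filter tests completeness of measurement, so it does nothing about a later drug. The off-treatment mark is not the start of new therapy and does not flag local treatment given on study drug. The waterfall has no such mark, and a listing does not correct a figure. Post-progression sums on study drug can stay.

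**Conclusion.** The point holds as a flaw in the rule for a descriptive figure. As written, the plots admit valid scans taken after subsequent anticancer therapy, and for the waterfall any resulting error favours the drug. The size in this trial cannot be computed, because the documents do not give the number of participants scanned after new therapy or after local treatment of a target lesion. The -40% against -10% comparison only illustrates how the rule works.

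A reader might infer more than this. One might conclude that the response rate is inflated; it is not, because BOR stops at further anticancer treatment, and DOR and primary PFS have the equivalent rule. One might also conclude that later shrinkage is in fact credited to the drug, or that a resected lesion automatically gives a deep bar. The documents support only that the first could happen, and they leave the second open.

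**What to change.** In SAP 14.1, for both plots and for both IRC and investigator reads:

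1. Use only valid sums from scans before the start of the first subsequent anticancer therapy, as defined in the Section 14.4 note, with its exception for palliative bone radiotherapy. The partial-date rule in Section 9 already covers these start dates.
2. Keep sums after progression while the participant is on study drug alone, so that true delayed shrinkage still shows.
3. For surgery or radiotherapy given while study drug continues, do not apply a blanket cut. Treat a timepoint as not valid if a target lesion was resected or irradiated, and keep the sums where only a non-target or new lesion was treated.
4. Identify treatment under item 3 from the concomitant procedures page as well. The after-discontinuation pages in Section 12.5 would not capture it.

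The cost is modest: extra programming across eCRF pages, matching of treated lesions to target lesions, and the loss of a few late points. If all scans are still wanted, show them in a supplementary plot with the post-therapy points flagged. No endpoint, test or sample size changes.

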#### 14.1.1 Subgroup analysis for BOR

Confirmed BOR, ORR and DCR according to RECIST 1.1 as adjudicated by IRC will also be evaluated on all subgroups as defined in Section 8.2. This will be repeated for Japanese participants including only the ADA and nAb status subgroup.

For ADA and nAb subgroups a listing will present the tumor assessment and overall response per RECIST 1.1 as assessed by the IRC including: participant ID, age, sex, race, ADA Status, nAb PD-L1 Assay Status, nAb TGF- $\beta$  Assay Status, visit, date(s) of imaging, description of target lesions (size, site, status, type, method, response), non target lesions (status, site, method, response), and new lesions (site, status, method), sum of lesion diameters, percent change in target lesions at baseline, and overall response. Two listings will be created: for the ADA positive participants and for nAb positive in either away (PD-L1 and TGF- $\beta$ ) participants.

Participants with missing subgroup category will not be included in the related subgroup analysis. Those subgroups analyses will be supported by forest plots.

#### 14.2 Best Overall Response according to RECIST 1.1 as assessed by Investigator (Secondary endpoint)

Analysis (Analysis Population)	Derivation	Statistical Analysis Methods	Missing data handling
Secondary endpoint: confirmed Objective Response (OR)			
Secondary analysis (ITT)	Confirmed Objective Response Rate (ORR) according to RECIST 1.1 as assessed by the Investigator is defined as the number of participants having a confirmed objective response assessment of Complete Response (CR) or Partial Response (PR) (at least two determinations of CR/PR at least 4 weeks apart and before progression), out of the total number of participants.	ORR will be provided with a two-sided 95% CI using the Clopper-Pearson method (exact CI for a binomial proportion as computed by default by the FREQ procedure using the EXACT option).	Participants with missing post-baseline data are considered as having a non-evaluable response

Data collected in the eCRF for RECIST 1.1 response criteria as assessed by the Investigator (“Assessment of disease based on imaging (according to RECIST 1.1)” eCRF page) will be treated in the same way as data adjudicated by the IRC. Analyses described in [Section 14.1](#) will be repeated based on Investigator assessment, i.e.:

- Number and percentage of participants with confirmed BOR of CR, PR, SD, PD and NE and corresponding listing
- ORR and DCR with their two-sided 95% CI
- Spider and Waterfall plots
- A summary table of the reasons for non-evaluable confirmed BOR and related listing, with the following reasons:
  - No baseline assessment (if applicable)
  - No post-baseline assessments due to death within 8 weeks after the start of study treatment
  - No post-baseline assessments due to other reasons
  - All post-baseline assessments have overall response ‘Non-evaluable’
  - New anticancer therapy started before first evaluable post-baseline assessment
  - SD of insufficient duration (<6 weeks after the start of study treatment)
  - No evaluable tumor assessment >16 weeks followed by PD (i.e. tumor assessment of PD was >16 weeks after start of study treatment and there was no evaluable tumor assessment in between)
  - Not determined category may also be added if applicable

All above analyses will be repeated for unconfirmed BOR.

In addition, a summary of the BOR (confirmed and unconfirmed) as adjudicated by IRC versus Investigator assessment will be provided included numbers of concordant and discordant assessment, and a listing of inconsistencies will be provided.

CCI

## 14.4

## Progression-Free Survival (Secondary Endpoint)

Analysis (Analysis Population)	Derivation	Statistical Analysis Methods	Missing data handling
Secondary endpoint: Progression-Free Survival (PFS)			
Secondary analysis (ITT)	Time from first administration of study treatment until the first documentation of progression of disease (PD) or death due to any cause, whichever occur first, per RECIST 1.1 as measured by the IRC.	Kaplan-Meier estimates (product-limit estimates) will be presented together with a summary of associated statistics (median time, 3-, 6-, 9-, 12-, 24-month rate estimates) including the corresponding two-sided 95% confidence intervals. The confidence intervals for the median will be calculated according to Brookmeyer and Crowley (1982) and confidence intervals for the survival function estimates at above defined timepoints will be derived using the log-log transformation according to Kalbfleisch and Prentice (2011) (conftype=loglog default option in SAS Proc LIFETEST). The estimate of the standard error will be computed using Greenwood's formula.	
PFS will be censored at the date of last progression-free tumor assessment or date of first study treatment, whatever is later.
 
Censoring rules (details provided in body text):
 

- No event (PD or death)

- No baseline and/or post-baseline assessment

- Start of new anticancer treatment

- Event after two or more subsequent missing response assessments

Sensitivity analysis 1 (ITT)			
PFS will be censored at the date of last tumor assessment with outcome CR, PR or SD or date of first study treatment, whatever is later.
 
Censoring rules (details provided in body text):
 

- No event (PD or death)

- No baseline and/or post-baseline assessment

Sensitivity analysis 2 (ITT)	Time from first administration of study treatment until the first documentation of progression of disease (PD) or death due to any cause, whichever occur first, per RECIST 1.1 as measured by the Investigator.	PFS will be censored at the date of last tumor assessment with outcome CR, PR or SD or date of first study treatment, whatever is later.
		
Censoring rules (details provided in body text):
 
 
- No event (PD or death)
 
- No baseline and/or post-baseline assessment
 
- Start of new anticancer treatment
 
- Event after two or more subsequent missing response assessments
 

Sensitivity Analysis 1: PFS counting all events (PD and death) regardless of the start of a new anticancer therapy and ignoring the number of missing evaluable tumor assessments before progression or death

Sensitivity Analysis 2: PFS as assessed by the Investigator

**Progression-Free Survival (PFS)** time is defined as the time from first administration of study treatment until the first documentation of progression of disease (PD) or death due to any cause, whichever occur first.

PFS = (date of PD or death or censoring – date of first administration of study treatment + 1)/30.4375 (months).

The following censoring rules will also be applied for the PFS computation:

- Participants with no event (PD or death) will be censored on the date of the last adequate tumor assessment
- Participants who do not have a baseline tumor assessment or who do not have any evaluable post-baseline tumor assessments will be censored at the date of first administration of study treatment unless death occurred on or before the time of the second planned tumor assessment (i.e. 16 weeks) in which case the death will be considered an event.
- Participants who start new anticancer treatment prior to an event will be censored on the date of the last evaluable tumor assessment before anticancer therapy is given.

Note: any systemic anticancer therapy, any anticancer surgery and any anticancer radiotherapy with exception of palliative bone radiotherapy will be considered as new/subsequent anticancer therapy and will lead to censoring.

- Participants with an event after two or more subsequent missing response assessments (i.e. no assessments in 112 days during the first 12 months of follow-up or 168 days after the first 12 months of follow-up) will be censored on the date of the last evaluable tumor assessment.

The last tumor assessment date is defined as the last available and evaluable tumor assessment performed prior to the cut-off date (or prior to end of study, i.e. participants lost to follow-up or who withdraw consent) or prior to subsequent anticancer therapy. If no evaluable tumor assessment is available, this date will be the date of first administration of study treatment.

Censoring rules are also summarized in [Table 5](#).

**Table 5** Censoring Rules for Primary and Sensitivity Analysis of PFS

Situation		Primary Analysis	Sensitivity Analysis 1	Sensitivity Analysis 2
No PD and no death	New anticancer therapy is not initiated	Censored at last tumor assessment*	Censored at last tumor assessment*	Censored at last tumor assessment*
	New anticancer therapy is initiated	Censored at last tumor assessment* before new anticancer therapy	Censored at last tumor assessment*	Censored at last tumor assessment* before new anticancer therapy
No baseline assessment or no evaluable post-baseline assessment	No death or death >16 weeks after start of study treatment	Censored at date of first administration of study treatment	Censored at date of first administration of study treatment	Censored at date of first administration of study treatment
	Death ≤16 weeks after start of study treatment	Progressed at date of death	Progressed at date of death	Progressed at date of death
PD or death	After ≤1 subsequent missing response assessment a	Progressed at date of document PD or death, whichever came first	Progressed at date of documented PD or death, whichever came first	Progressed at date of documented PD or death, whichever came first
	After ≥2 subsequent missing response assessment a	Censored at last tumor assessment* before missing assessments.	Progressed at date of documented PD or death, whichever came first	Censored at last tumor assessment* before missing assessments
	Before started new anticancer therapy	Progressed at date of document PD or death, whichever came first	Progressed at date of documented PD or death, whichever came first	Progressed at date of document PD or death, whichever came first
	After started new anticancer therapy	Censored at last tumor assessment* before new anticancer therapy	Progressed at date of documented PD or death, whichever came first	Censored at last tumor assessment* before new anticancer therapy

Sensitivity Analysis 1: PFS counting all events (PD and death) regardless of the start of a new anticancer therapy and ignoring the number of missing evaluable tumor assessments before progression or death

Sensitivity Analysis 2: PFS as assessed by the Investigator

\* with outcome CR, PR or SD. If no adequate tumor assessment, censored at date of first administration of study treatment

a No assessments in 112 days during the first 12 months of follow-up or 168 days after the first 12 months of follow-up

PFS according to RECIST 1.1 as measured by the IRC will be described (secondary endpoints).

The analysis of PFS will be performed with a Kaplan-Meier method (product-limit estimates) and a summary of associated statistics will be presented including corresponding two-sided 95% CIs. The CIs for the median will be calculated according to Brookmeyer and Crowley (1982) and CIs for the survival function estimates will be derived using the log-log transformation according to Kalbfleisch and Prentice (1980) (CONFTYPE=loglog default option in SAS PROC LIFETEST). The estimate of standard error will be computed using Greenwood's formula.

Frequency (number and percentage) of participants with and without event and within each event type (PD or death) will be presented as well as the PFS median, min and max. Number of participants at risk, failed and PFS rates with their CI at 6, 12 and 24 months will also be provided. Censoring reasons will also be described. Censoring reasons are as follows:

- Administrative censoring (ongoing in the study without an event)
- No baseline assessment
- No evaluable post-baseline assessment
- Start of new anticancer therapy
- Event after 2 or more missing or non-evaluable post-baseline assessments
- Withdrawal of consent
- Lost to follow-up

Lost to follow-up will include the following participants:

- Lost to follow-up status is collected on the eCRF treatment termination page or eCRF study termination page prior to the analysis cut-off
- Participants with the last alive date > 14 weeks prior to the analysis cut-off date (duration of 14 weeks is based on the assessment schedule of every 3 months for survival follow-up interval + 2-weeks window)

PFS will also be presented graphically with Kaplan-Meier figures.

Separate listings will be provided for the different assessment methods with the following information: participant identifier, age, sex, race, date of first administration of study treatment, date of last tumor assessment, date of event/censoring, event/censoring reason, time to event.

